6.2. Secondary Endpoint(s)

6.2.1. Binary endpoints

Endpoints: ASAS 40, ASAS 20, ASAS 5/6, , BASDAI50, the proportion of subjects with ASAS partial remission, the proportions of subjects with ASDAS inactive disease, major improvement and clinically important improvement, the proportion of subjects with at least 1 dactylitic digit, the proportions of subjects with any or persistent peripheral articular involvement EQ-5D index improvement ≥ 0.5 , EQ-5D VAS score > 82 , each EQ-5D item proportion reporting “no problem”, WPAI proportion employed, SF-36 PCS and MCS improvements of ≥ 2.5 and ≥ 5.0 .

- Analysis time points: All Period 1, 2 and 3 scheduled visits.
- Analysis population (method of imputation for missing data): FAS (LOCF and observed cases), where FAS populations are defined in each period in [Section 4.1](#).
- Analysis methodology: Proportions will be summarized using the methods specified in [Section 5.2.1](#).
- Supporting objective and Decision rule: Secondary Objectives.

Reporting results:

- Descriptive: The number evaluated, percent with response of interest and 95% confidence intervals. For response endpoints defined using change from baseline (eg, ASAS40) period 1 baseline will always be used as the reference point.

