The BASDAI 50 endpoint is defined as the proportion of subjects who achieved a 50% improvement (decrease) from baseline in their BASDAI score.

- High sensitivity C Reactive Protein (hsCRP);

The lab value of hsCRP will be evaluated as both a continuous endpoint as proportion normal at each visit.

Health Outcomes Assessments using the following instruments:

- EuroQoL-5D Health Questionnaire (EQ-5D).

There are 5 questions in the EQ-5D, one for each dimension of health (mobility, self care, usual activities, pain/discomfort and anxiety/depression). Each question has three possible responses (no problem in the relevant health dimension to severe problems). If a patient reports no problem in any health dimension, then his EQ-5D score is 1. Otherwise, the EQ-5D index is calculated following the table below, with the amount shown for each response subtracted from a starting (perfect health) score of 1.

| EuroQol dimension | Response = 2 | Response = 3 |
|--------------------|--------------|--------------|
| Mobility | 0.069 | 0.314 |
| Self-care | 0.104 | 0.214 |
| Usual activity | 0.036 | 0.094 |
| Pain/discomfort | 0.123 | 0.386 |
| Anxiety/depression | 0.071 | 0.236 |
| Any response level | 0.081* | 0.269 |

* Subtracted if any score of 2 or 3 is present – if a score of 3 is present, both 0.081 and 0.269 are subtracted.

For example, if a subject has EQ-5D assessment scores of 1, 1, 2, 2 and 3 for the 5 dimensions, the utility weight would be:

- Full Health =1.000
- Constant term (for any dysfunctional state) -0.081
- Mobility (level 1) -0
- Self-Care (level 1) -0
- Usual Activities (level 2) -0.036
- Pain or discomfort (level 2) -0.123
- Anxiety or depression (level 3) -0.236
- Any dimension at level 3 -0.269

Therefore, the estimated value for 11223 is $1-0.081-0-0-0.036-0.123-0.236-0.269 = 0.255$

EQ-5D score will be defined as missing if one or more items are missing.

In addition to the 5 questions above, there is a separate question about overall health state measured on a 0 to 100 mm scale where 0 = worst imaginable health state and 100 = best imaginable health state.

In addition to the continuous scores, the following dichotomous endpoints will be summarized:

- Proportion with EQ-5D VAS score of >82 (population norm)
- Proportion with EQ-5D index improvement from baseline of ≥ 0.05
- Proportion of each EQ-5D item score (5 total) reporting ‘no problem’

- SF-36

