3.3. Other Endpoints

3.3.1. Non-steroidal Anti-Inflammatory Drug (NSAID) Usage

Any NSAIDs taken as background medications during the study will be identified along with start and stop dates, average daily dose (mg) and treatment frequency (days per week). Details regarding the calculation can be found in [Appendix 1.1](#). This intake score will be calculated for each study period.

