9. APPENDICES

Appendix 1. DATA DERIVATION DETAILS

Appendix 1.1. Calculation of NSAID Intake Total Score

The general formula for calculation of the NSAID intake total score is:
 (equivalent NSAID score) × (days of intake during period of interest) × (days per week) /
 (period of interest in days).

The equivalent NSAID score in this formula can be obtained from the table below. The table shows the doses of various commonly used NSAIDs that are considered equivalent to a 150 mg dose of diclofenac. A 150 mg daily would be used to achieve optimal symptomatic control of a patient with axial SpA. Diclofenac 150 mg is assigned a score of 100. The equivalent score for other NSAIDs can be determined based on their dose. A 20 mg dose of piroxicam, since it is equivalent to a 150 mg dose of diclofenac is also assigned a score of 100. A 1200 mg dose of ibuprofen would have a score of 50 (since it is half of the equivalent dose).

| NSAID | Dose (mg) comparable to 150 mg of diclofenac |
|----------------|--|
| Diclofenac | |
| Naproxen | 1000 |
| Aceclofenac | 400 |
| Celecoxib | 200 |
| Etodolac | 600 |
| Etoricoxib | 90 |
| Flurbiprofen | 200 |
| Ibuprofen | 2400 |
| Indometacin | 150 |
| Ketoprofen | 200 |
| Meloxicam | 15 |
| Nimesulide | 200 |
| Phenylbutazone | 400 |
| Piroxicam | 20 |
| Tenoxicam | 20 |

As an example, suppose a 12 week period from baseline through week 12 (84 days) is of interest. During this period, a subject took piroxicam 4 times a week at a dose of 20 mg for the first 8 weeks and then switched to ibuprofen 2 times a week at a dose of 1200 mg for the last 4 weeks. Based on the table, the equivalent score for 20 mg of piroxicam is $[100 \times 56 \times (4/7)]/84 = 38.1$, and the score for ibuprofen is $[50 \times 28 \times (2/7)]/84 = 4.8$.

The NSAID intake score for this subject for this 12 week period is $38.1 + 4.8 = 42.9$.

Notes:

Follow up based on NSAIDS identified in the study but not included in the table above:

Lornoxicam – assigned the same dose equivalence as Piroxicam in the table

Alternative names for known medications were mapped as follows (unknown/known):

| |
|---------------------------------------|
| Olfen Uno/diclofenac |
| Orudis Retard/ketoprofen |
| Orudis depot/ketoprofen injection |
| Orudis Retard/ketoprofen |
| Salsalate/disalcid |
| Surgam/tiaprofenic acid |
| Trosicam/meloxicam |
| Xefo Rapid/lornoxicam |
| Xefo rapid/loroxicam |
| diclofenac/dicolfenac |
| diclofenacum natricum/diclofenac |

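### Two SAP derivation rules conflict with the SAP's own text: the EQ-5D index response cut-off (0.5 against 0.05) and the NSAID intake formula (no division by 7)

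*SAP*

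**What the plan says.** **EQ-5D index response.** SAP Section 3.2 gives the scoring table and then lists the dichotomous endpoints, among them "Proportion with EQ-5D index improvement from baseline of ≥ 0.05". SAP Section 6.2.1, which names the binary endpoints to be tabulated, gives it as "EQ-5D index improvement ≥ 0.5". Nothing in the SAP describes two separate index thresholds, and the protocol gives none.

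**NSAID intake score.** SAP Section 3.3.1 says that background NSAIDs will be recorded with "average daily dose (mg) and treatment frequency (days per week"), so frequency is held as a count such as 4. It adds that the score will be calculated for each study period. The general formula in Appendix 1.1 multiplies ("equivalent NSAID score) × (days of intake during period of interest) × (days per week") and divides by the length of the period in days. In the example below it, "a subject took piroxicam 4 times a week at a dose of 20 mg for the first 8 weeks", then ibuprofen 1200 mg twice a week for the last 4 weeks of a 12-week period. That example uses 4/7 and 2/7 as the frequency terms and reaches a total of 42.9.

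Neither conflict comes from superseded text. The SAP's change table records only added NSAID classifications for Appendix 1.1, plus general typographical corrections.

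**The concern.** A programmer who works from Section 6.2.1 will code a threshold ten times the one in the definition section. The EQ-5D responder proportion is to be reported with a 95% confidence interval at scheduled visits in all three periods, under both LOCF and observed cases, so one wrong threshold would run through many table cells.

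For NSAID intake, the appendix gives a daily diclofenac dose of 150 mg a score of 100. The printed formula does not respect that anchor and does not reproduce the SAP's own example. Coded literally, every score is multiplied by 7.

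**Working it through.** **1. NSAID score: reproduce the SAP's figure.** Inputs from Appendix 1.1: piroxicam 20 mg has score 100, span 56 days, 4 days per week; ibuprofen 1200 mg has score 50, span 28 days, 2 days per week; the period is 84 days.

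With days per week / 7:
- Piroxicam: 100 × 56 × (4/7) / 84 = 38.1
- Ibuprofen: 50 × 28 × (2/7) / 84 = 4.8
- Total: 42.9, which agrees with the SAP.

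**2. NSAID score: the formula as printed.** With days per week and no 7:
- Piroxicam: 100 × 56 × 4 / 84 = 266.7
- Ibuprofen: 50 × 28 × 2 / 84 = 33.3
- Total: 300.0, and 300.0 / 42.86 = 7.

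**3. NSAID score: check against the anchor.** Full equivalent dose every day for the whole period:
- With / 7: 100 × 84 × (7/7) / 84 = 100
- As printed: 100 × 84 × 7 / 84 = 700

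The example and the anchor both point to an omitted division by 7.

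**4. NSAID score: meaning of days of intake.** The example uses the calendar span on each drug (56 and 28), which the formula does not say. If the 7 is added but days actually dosed are used (8 × 4 = 32 and 4 × 2 = 8), frequency enters twice: 100 × 32 × (4/7) / 84 + 50 × 8 × (2/7) / 84 = 21.8 + 1.4 = 23.1 (components rounded), not 42.9.

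**5. EQ-5D: reproduce the SAP's figure.** With the Section 3.2 table, state 11223 = 1 − 0.081 − 0.036 − 0.123 − 0.236 − 0.269 = 0.255, which agrees with the SAP's example.

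**6. EQ-5D: what each cut-off demands.**
- Worst state with no level-3 answer, 22222: 1 − 0.081 − 0.069 − 0.104 − 0.036 − 0.123 − 0.071 = 0.516. Its largest possible gain is 1 − 0.516 = 0.484, which is below 0.5. No subject without a level-3 answer at baseline can respond at 0.5.
- The SAP's example state 11223 (0.255) improving to 11222 (1 − 0.081 − 0.036 − 0.123 − 0.071 = 0.689) gains 0.434: a responder at 0.05, not at 0.5.
- The 0.5 cut-off is not impossible in general: 11131 (1 − 0.081 − 0.269 − 0.386 = 0.264) to 11121 (1 − 0.081 − 0.123 = 0.796) gains 0.532.

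**7. EQ-5D: count over all 3^5 = 243 states.** The table shows the number of baseline states from which some improvement meets the cut-off.

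| Baseline states | Number | At 0.05 | At 0.5 |
|---|---|---|---|
| No level-3 answer | 32 | 31 | 0 |
| At least one level-3 answer | 211 | 211 | 210 |
| All | 243 | 242 | 210 |

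The state that fails at 0.05 is 11111, which cannot improve. The one level-3 state that fails at 0.5 is 11311 (0.556, largest gain 0.444). These are counts of health states, not of subjects.

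**The case against.** The best case against the point concerns its weight, not its facts.

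- **The NSAID slip largely corrects itself.** The example sits directly under the formula, and a score of 700 for a daily full dose would look wrong at once. Anyone validating code against the example would find it. This stands as a reason for low severity, but the printed rule is still wrong.
- **The wording on days of intake is not an error.** The example already shows that the calendar span is meant. This also stands: the 23.1 shows how the phrase could be misread, and the remedy is only a clarification.
- **Little depends on either rule.** The NSAID score is not named among the endpoints in Sections 6.2.1 and 6.2.2, and is neither a Cox covariate nor a subgroup factor. The EQ-5D cut-off is an SAP addition to a descriptive endpoint in a study without hypothesis tests, and the index is also summarised as a continuous variable. All of this is correct.
- **The state counts say nothing about the actual responder rate.** True: they show that the cut-offs behave differently, not by how much in this population.

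What these arguments do not remove is the EQ-5D contradiction. No worked example settles 0.5 against 0.05, and Section 6.2.1 is the section that specifies the analysis.

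**Conclusion.** Both contradictions are real and lie within the current SAP. Severity is minor.

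For the NSAID score, the printed formula is 7 times too large, and the SAP's own example and anchor show what was meant. Because 7 is a constant factor, relative comparisons between subjects or periods would survive; the scores themselves would not.

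For EQ-5D, the cut-offs differ tenfold, and the larger one excludes every subject with no level-3 answer at baseline. The change in the responder proportion cannot be calculated without the baseline distribution of states. A dropped zero in Section 6.2.1 is the likeliest explanation, because Section 3.2 is the definition section, but the documents do not prove which value was intended.

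The primary flare estimate, time to flare and sample size are unaffected.

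**What to change.** - **SAP Section 6.2.1:** change the EQ-5D index cut-off from 0.5 to 0.05 to match Section 3.2, with the sponsor confirming that 0.05 is intended.
- **SAP Appendix 1.1:** print the frequency term in the general formula as days per week / 7.
- **SAP Appendix 1.1, as a clarification:** state that days of intake means the calendar span on the drug, as in the worked example.

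The cost is two one-line corrections and one phrase. No new data are needed and the primary analysis does not change.

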### **9.2.2. Analysis of Secondary Endpoints**

For the key secondary endpoint of time to flare, descriptive statistics will include median time to flare and 95% confidence interval using the Kaplan-Meier approach. In addition an estimate of the relative flare rates in the current study and that seen in those subjects in protocol B1801031 who met the treatment withdrawal criteria for the current protocol will also be obtained; subjects in B1801031 did not discontinue treatment and will serve as a reference population. For this estimate a Cox Proportional Hazards model will be used. A 99% confidence interval will be calculated for the Hazard Ratio. Additional sensitivity analyses evaluating the impact of covariates may be performed, details will be provided in the statistical analysis plan.

The efficacy upon retreatment will be assessed descriptively as the proportion of subjects who achieve an ASDAS CRP inactive disease less than 1.3; this will be expressed as a percent with 95% confidence interval.

Dichotomous clinical and subject rated endpoints measured during Periods 1 and 2 will be summarized as number evaluated, percent with response of interest and 95% confidence intervals.

For continuous clinical and subject rated endpoints measured during Periods 1 and 2, both raw and change values will be summarized with the following descriptive statistics: n, mean, standard deviation, min and max, median and the 25th and 75th percentiles (quartiles).

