4. ANALYSIS SETS

4.1. Full Analysis Set

4.1.1. Period 1

The full analysis set for period 1 will include all subjects who took study medication and had one evaluation after baseline.

4.1.2. Period 2

The full analysis set for period 2 will include all subjects who had at least one evaluation during period 2.

4.1.3. Period 3

The full analysis set for period 3 will include all subjects who took study retreatment medication and had at least one evaluation after restarting active therapy.

4.2. 'Per Protocol' Analysis Set

A per-protocol population may be defined for sensitivity analysis of the primary and key secondary efficacy endpoints (ASDAS inactive disease, ASAS 40). This will be defined separately for the withdrawal and retreatment periods. The per-protocol populations will be defined as subsets of each FAS population excluding subjects who have a protocol violation that is thought to potentially affect efficacy, with focus on potential violations of inclusion criteria in each period. There will be no per protocol population defined for period 1 of the study.

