5.3. Methods to Manage Missing Data

Unless otherwise specified, missing items for observations on the individual items of the derived efficacy and health outcome scales will be handled as follows. If more than 20% of the items are missing, the total scores for these scales will be considered missing. If 20% or fewer items are missing, the average of the available items will be multiplied by the total number of items to get a derived total score. Similarly, if more than 20% of the items from a subscale are missing the subscale will not be used in the analysis. If 20% or fewer items are missing then the average of the available items for that subscale will be multiplied by the total number of items in the subscale to get the derived subscale score.

Where an observed case analysis is being employed, the data will be analyzed without imputation for missing visit data. Where the last observation carried forward (LOCF) approach is being employed, efficacy assessments will be handled in the following manner. If the scheduled assessment is available it will be used. If the scheduled assessment is missing, the immediately preceding assessment, scheduled or unscheduled, will be used (eg, if assessments are to be done at weeks 4, 8 and 12 and data are available at weeks 4 and 12 but week 8 is missing, then the week 4 value will be carried forward to week 8). Baseline data will not be carried forward unless otherwise noted. For composite endpoints, missing components will not be carried forward to complete a composite endpoint with partial data available; only the complete composite endpoint value will be carried forward.

Missing values for safety endpoints will not be imputed.

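### SAP 6.2.1 plans only LOCF and observed cases for the response endpoints; add non-responder imputation on fixed denominators, and label Period 2 observed-case rates as conditional on staying in Period 2

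*SAP*

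**What the plan says.** SAP 6.2.1 covers all the binary secondary endpoints together. The population and missing-data rule is "FAS (LOCF and observed cases"), with the populations set by period in SAP 4.1, and the timing is "Analysis time points: All Period 1, 2 and 3 scheduled visits". The report gives "The number evaluated, percent with response of interest and 95% confidence intervals".

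SAP 5.3 defines the two methods:
- **Observed cases:** "Where an observed case analysis is being employed, the data will be analyzed without imputation for missing visit data". A subject without a value at a visit is therefore not in that visit's denominator.
- **LOCF:** "If the scheduled assessment is missing, the immediately preceding assessment, scheduled or unscheduled, will be used". Baseline is not carried forward.

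SAP 4.1 sets the populations. The Period 3 full analysis set is those who "took study retreatment medication and had at least one evaluation after restarting active therapy"; Period 1 has a matching requirement. The Period 2 set needs only one Period 2 evaluation, so subjects who flare stay in it.

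Under SAP 2.2.3, a subject who flares moves to retreatment and has no later Period 2 visits. SAP 3.4 makes the last value before retreatment a Period 2 value, and measures every change-based response from Period 1 baseline.

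Protocol 9.2.2 describes retreatment efficacy as "the proportion of subjects who achieve an ASDAS CRP inactive disease less than 1.3", with a 95% interval and no missing-data rule. Neither document mentions non-responder imputation.

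**The concern.** The study only estimates (SAP 5.1), so each proportion is only as clear as its denominator. Under observed cases the denominator shrinks with every dropout. In Period 2 it also shrinks with every flare, which is the event the trial is designed to count. A late Period 2 table of inactive disease or ASAS response could then suggest that most subjects stay well off drug, when it describes mainly those who have not yet flared.

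LOCF avoids that problem but has a smaller one of its own. A subject who leaves while responding, for instance after a serious infection or missed doses (Protocol 6.8), stays a responder to the end of the period. Subjects treated in Periods 1 or 3 with no later evaluation appear in neither method.

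Retreatment response matters most, because it is one of the two rates that Protocol 9.1 uses to size the study. Protocol 9.1 plans that rate over everyone who flares and restarts treatment, which neither planned method is sure to estimate.

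**Working it through.** **Inputs from Protocol 9.1.** About 200 enrolled; about 96 enter Period 2; 70% flare; 60% of retreated flarers regain inactive disease.

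**Assumptions, because the documents give no figures.** Dropout of 5-15%; 50%, 70% or 90% of non-flarers inactive at Week 64; all flares before the Week 64 window opens (Day 421, SAP Appendix 2.3).

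**1. The plan's own figures.** Half-width = 1.96 × √(p(1−p)/n).
- Flare: p = 0.70, n = 96 gives 9.2 points (stated: about 10).
- Retreatment: n = 0.70 × 96 ≈ 67, p = 0.60 gives 11.7 points (stated: about 12).

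Both reproduce. The second does so with all 67 expected flarers in the denominator.

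**2. Period 2, Week 64 inactive disease.** 67 flare and 96 − 67 = 29 do not. With no other dropout:

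| Non-flarers inactive | Observed cases | All 96 entrants | LOCF, flare value a non-response |
|---|---|---|---|
| 50% | 14/29 = 48% | 15% | 15% |
| 70% | 20/29 = 69% | 21% | 21% |
| 90% | 26/29 = 90% | 27% | 27% |

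The ratio of observed cases to all entrants is 96/29 = 3.3. LOCF matches non-responder imputation here because flarers stay in the Period 2 set and their flare value is carried.

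Now let 10 of the 29 non-flarers also drop out, with 13 of the remaining 19 inactive. Observed cases give 13/19 = 68% and non-responder imputation 13/96 = 14%. LOCF gives from 13/96 = 14% to 23/96 = 24%, depending on how many of the 10 left while inactive.

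**3. When a carried flare value still counts as a response.**
- SAP 3.2 sets clinically important ASDAS improvement at a fall of at least 1.1 from baseline. A subject going from 3.4 at Period 1 baseline to 2.2 at flare has fallen by 1.2 and still qualifies. ASAS 20/40 and BASDAI50 leave the same opening.
- Flare uses ASDAS ESR, while inactive disease uses ASDAS CRP. Take ESR 40 mm/h, all four items at 1 cm and CRP set to 2. ASDAS ESR = 0.35 + 0.29√40 = 2.18. ASDAS CRP = 0.362 + 0.579 ln 3 = 1.00. This subject has flared and is also inactive.

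**4. Period 1 inactive disease at Week 24.** The fixed-denominator rate is 96/200 = 48%.

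| Dropout | Observed cases | LOCF, none to all dropouts responding at last value |
|---|---|---|
| 5% | 96/190 = 50.5% | 48-53% |
| 10% | 96/180 = 53.3% | 48-58% |
| 15% | 96/170 = 56.5% | 48-63% |

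**5. Period 3 inactive disease, n = 67.** Dropout of 5, 10 or 15% is 3, 7 or 10 subjects.
- If 60% is the observed-case rate, non-responder imputation gives 0.60 × 64/67 = 57.3%, 0.60 × 60/67 = 53.7% or 0.60 × 57/67 = 51.0%. LOCF spans 57.3-61.8%, 53.7-64.2% or 51.0-66.0%.
- If 60% is the rate over all retreated, as Protocol 9.1 reads, non-responder imputation gives 60%. Observed cases then give 40.2/64 = 62.8%, 40.2/60 = 67.0% or 40.2/57 = 70.5%.

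On the first reading the gap reaches 9 points against a half-width of about 12. The half-width hardly changes (11.8-12.0 points), so the interval would not reveal it.

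**The case against.** A reader might infer that both planned methods are optimistic, that LOCF counts dropouts as responders, and that Period 2 responses are scored among non-flarers only. The documents do not support this. LOCF carries the last value whether good or bad and never carries baseline. The early discontinuation visit (Protocol 6.7) seeks full assessments, so the carried value may be the exit status. Flarers remain in the Period 2 set. For inactive disease, LOCF is therefore right about nearly all flarers.

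The 69% versus 21% contrast is also the extreme case. Subjects can flare at Week 64 itself, and SAP Appendix 2.3 runs that window from Day 421 to the end of Period 2, so some flarers will be counted there. The factor of 3.3 is an upper bound.

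Further points have weight:
- SAP 6.2.1 reports the number evaluated, so a shrinking denominator is visible.
- The disposition tables (SAP 6.3.2, 6.5.2) give the numbers entering each period. Because Period 2 entry requires inactive disease at Week 24 (Protocol 4.2), they come close to the fixed-denominator Period 1 rate.
- Non-responder imputation is a lower bound by construction, and counting flare as non-response changes what is estimated. That LOCF exceeds it does not prove LOCF wrong.
- These are secondary endpoints in a study without hypothesis tests.

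These points rule out calling the planned methods invalid. They do not supply the missing rate. The disposition tables give no fixed-denominator retreatment rate, and none for ASAS or BASDAI50.

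**Conclusion.** The point holds as a gap in the planned set of analyses. The serious distortion belongs to observed cases at late Period 2 visits: up to 69% against 21%, if 70% flare before the Week 64 window and 70% of the rest are inactive. LOCF corrects most of it for inactive disease. It remains open to carrying a past response for subjects who leave while responding, and for flarers who still meet an endpoint measured from Period 1 baseline. Its equality with 21% also assumes that Period 2 visits after the move to Period 3 count as missing and are filled from the flare visit; SAP 5.3 implies this but does not say it.

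In Periods 1 and 3 the effect is moderate and rests wholly on the assumed 5-15% dropout: observed cases of 51-56% against 48% in Period 1, and 57-51% by non-responder imputation for a 60% observed-case rate in Period 3. The primary flare proportion, the Kaplan-Meier and Cox analyses, and the sample size are not affected.

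**What to change.** In SAP 6.2.1, add a prespecified non-responder-imputation analysis for the response endpoints only: ASAS 20, ASAS 40, ASAS 5/6, ASAS partial remission, ASDAS inactive disease, ASDAS major and clinically important improvement, and BASDAI50.

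- **Denominators:** all treated subjects in Period 1, all entrants in Period 2, all retreated subjects in Period 3.
- **Rule:** discontinuation counts as non-response from then on; in Period 2, flare also counts as non-response from then on.
- **Place:** report it alongside LOCF. Make it the lead estimate for retreatment ASDAS inactive disease, to match the rate on which Protocol 9.1 sizes the study.
- **Labelling:** mark Period 2 observed-case rates as conditional on remaining in Period 2.
- **Clarification:** state in SAP 5.3 whether LOCF fills Period 2 visits after the move to Period 3.

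Do not apply it to dactylitis, peripheral articular involvement or employment, which are not responses.

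The cost is one extra table set and no new data. Reported rates will be somewhat lower in Periods 1 and 3, and much lower than observed cases late in Period 2.
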